2.4.2. Internet delivery of behavioral weight control program

Participants will have access to behavioral lessons weekly. The standard version of the lesson is very visual, capitalizing on the capabilities of the internet delivery. We will be notified over the Web site when participants have completed lessons and we will, therefore, be able to electronically assess compliance with this program component

All potential participants will be given an orientation to the website and MyFitnessPal at Visit 1 prior to entering the weight loss program. We will assess compliance with asthma and food diary entries at Visit 2, only participants who have completed diary requirements (same 3 days of asthma and food diaries) will be considered eligible to continue in study.

Participants will be enrolled into a “group” at Visit 2, although they will not meet in-person and this “group” will be maintained throughout an individual’s study participation. Groups will be homogenous with respect to language (English or Spanish). Participants will have access to the Internet site and will be assigned a group on-line chat time. The group facilitator will e-mail them weekly, and they will be encouraged to use various components of the Web site. Individual usage of the site will be tracked by username through server activity logging and the use of WebTrends (NetIQ Corporation, San Jose, CA) log analysis software.

Participants will have access to new behavioral lessons each week. Participants will be provided with a computer. We will provide them with a data plan or hot-spot for internet access if they do not have internet access.

2.4.3. Promoting adherence to the online weight control intervention

We encourage adherence by tailoring the intervention expectations to shape an individual’s behavior such that it approaches the intervention goals. For example, individuals who are having difficulty self-monitoring are given options to make it easier, walking them through how to develop their own shortcuts to self-monitoring (the “my pantry” option on the website), having a short term goal of recording just a few days a week or only specific meals of the day, etc. Individuals who miss a group chat session will be contacted by email promptly. Lesson materials are available for those who miss the chat, and summaries of the missed session. We use a problem-solving approach to barriers to attendance. We have found this comprehensive and proactive approach to adherence promotion to be effective in maintaining high levels of study participation.

2.4.4. Online weight control facilitator

[name] has trained a cadre of experienced facilitators who have conducted the online weight control program. Online weight control interventionists on our research team at present include registered dieticians, masters-level health behavior experts, and doctoral level psychologists. Thus, our online intervention team is multi-disciplinary, skilled in conducting behavioral weight loss treatment programs, and ethnically diverse. The interventionist will be directly supervised by [name].

2.4.5. Intervention training and fidelity monitoring

Our previous experience in obesity treatment outcome research suggests that the following quality procedures will help ensure treatment fidelity:

1. Development of detailed intervention protocols;
2. Careful training, certification, and periodic re-training;
3. Periodic observation of intervention delivery to ensure protocol adherence and to provide corrective feedback;
4. Documentation of all intervention contacts to monitor participant exposure to treatment; and
5. Regular project meetings to review overall conformity to structured protocols and prevent any drift between interventionists.

2.4.6. Assembling weight control cohorts

The intervention requires that 5-10 participants form a group to participate in the weekly group chat sessions. A group may include participants from both sites. The group will essentially be a cohort of participants starting and ending the study at the same time. Because it is essential that the V1 and V2 visits be conducted close together, the cohorts need to be assembled prior to starting the study. Individuals who are interested in the study will be directed to the PLAN website to complete a study registrations form. The form will include individuals' names, contact information, basic eligibility information, information on the days of the week and times that a person will be consistently available for group chat sessions, preferred language (English or Spanish), and the center. These data may be collected prior to an individual providing consent for the study. The registration form will include text briefly describing study and how the information provided on the registration form will be used. Clinical center personnel will only be able to see the data from individuals who selected their center for attending study visits. The central coordinator will be able to view registration data from both sites in order to assemble the cohorts of 5-10 individuals who can participate in group chats at the same time. Once there are sufficient individuals who can participate in group chats at the same or similar times, the central coordinator will contact the clinical center coordinator to schedule V1 and V2 visits for these individuals. If the individual has not provided consent, consent will be obtained at the V1 visit before screening. Once all the cohort has completed V2, the coaches will contact cohort members to schedule the first chat. The goal is for the first chat session to take place in the 2 weeks following V2.

2.5. Statistical considerations

2.5.1. Data analysis

The appropriateness of the human, technological and systems components of the data acquisition and management procedures will be analyzed including practicality of data acquisition, estimation of likely participant characteristic and outcome distributions, suitability and functionality of paper and electronic forms, and resources required for participants contact and follow up, and to anticipate rates for missing data. Secondary analyses will include adjustments for different degrees of self-reported exercise.

2.5.2. Sample size

The decision to proceed to the full scale trial will be based on a futility design analysis, which guided our sample size estimates. We will determine this study as futile if we cannot produce a clinically significant weight loss in a significant proportion of participants. A clinically significant weight loss is set at 5% (which is the amount of weight that appears to be necessary to improve asthma control based on previous studies, and also the amount of weight loss required for FDA approval of a weight loss medication). A significant proportion of the population is set at 35% (FDA recommend that a weight loss medication must produce a 5% weight loss in 35% of participants to be considered effective).³¹

A straightforward way to test for futility with a binary outcome is based on the binomial distribution³². For a given minimum sufficient efficacy (p_1) and level that would indicate the intervention was ineffective (p_0), the threshold for continuing, c , can be determined for any sample size, n , as follows: the largest value of c such that $P(X \geq c | p_0) \leq \alpha$, type I error, and $P(X \geq c | p_1) \geq 1-\beta$, power, i.e. minimize the type II error. Ineffective thresholds of 5% and 10% were considered (Table 2). To be conservative, drop-outs will count as weight loss failures. With 40 patients, we have 94% power and $\alpha < 0.001$ using a threshold of 9 and assuming $p_0 = 0.1$ vs $p_1 = 0.35$, i.e. if ≥ 9 individuals have clinically significant weight loss we would reject futility and continue on to a larger trial. For the 12 Hispanics, we would need ≥ 3 ($\alpha = 0.026$, $1-\beta = 0.87$) and ≥ 2 ($\alpha = 0.02$, $1-\beta = 0.85$) individuals to achieve 5% weight loss reject futility assuming $p_0 = 0.1$ vs $p_1 = 0.45$ and $p_0 = 0.05$ vs $p_1 = 0.35$, respectively.

Table 2: Power, type I error, and threshold for rejecting futility for a variety of futility, p_0 , and minimum efficacy, p_1 , thresholds

p_0	p_1	c	$N = 40$	p_0	p_1	c	$N = 12$
			$\alpha, 1-\beta$				$C, \alpha, 1-\beta$
0.1	0.25	6	0.013, 0.96	0.10	0.40	2	0.11, 0.92
		7	0.003, 0.90			3	0.026, 0.77
		8	< 0.001, 0.82			4	0.004, 0.56
	0.30	7	< 0.001, 0.94		0.45	2	0.11, 0.96
		8	< 0.001, 0.89			3	0.026, 0.87
		9	< 0.001, 0.80			4	0.004, 0.70
	0.35	9	< 0.001, 0.94	0.05	0.35	1	0.12, 0.96
		10	< 0.001, 0.88			2	0.020, 0.85
		11	< 0.001, 0.79			3	0.002, 0.65

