1.4. Overview of study design

This will be a pilot study of a weight loss intervention at two centers, the University of Arizona and the University of Vermont. The primary outcome of interest will be the percent of participants achieving a 5% weight loss, which is the amount of weight loss that prior studies suggest is required to improve asthma control.

This will be a single arm-phase II futility trial; the “futility” to be assessed is the ability to produce weight loss. Such designs are widely used in efficiently informing decisions to proceed to Phase III clinical trials. This trial design is appropriate when the effect of the placebo arm can reasonably be estimated (weight loss is likely to be close to 0), and the toxicity of the treatment is minimal (no toxicity is anticipated related to weight loss).¹⁸ Therefore, this will be a single arm 6-month study of 40 participants (20 at each site). All participants will be assigned to the weight loss intervention, which is described in detail below.

2. Methods

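### The main go/no-go rule (at least 9 of 40) has type I error 0.0155 and power 97% at p0 = 0.10 and p1 = 0.35, not the stated <0.001 and 94%

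*Combined protocol and SAP*

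**What the plan says.** Section 1.4 describes the trial in these terms: "this will be a single arm 6-month study of 40 participants (20 at each site"; its primary outcome is the percentage of participants who lose 5% of body weight. Section 2.5.2 makes the decision on the full trial rest on a futility analysis of that outcome. It introduces the method thus: "A straightforward way to test for futility with a binary outcome is based on the binomial distribution". It defines type I error as the probability of c or more successes under p0, and power as the same upper tail under p1. Drop-outs count as failures, so the denominator stays at 40.

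The design statement is: "With 40 patients, we have 94% power and $\alpha < 0.001$ using a threshold of 9 and assuming" p0 = 0.1 against p1 = 0.35. The same sentence restates the rule with an inclusive inequality: at 9 or more, "individuals have clinically significant weight loss we would reject futility and continue on to a larger trial". Table 2 repeats the figures in its N = 40 row for p0 = 0.1, p1 = 0.35, c = 9.

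**The concern.** The section fixes n, c, p0, p1, the direction of the inequality and the definition of both error rates, so the stated alpha and power can be checked without any assumption. They fail the check.

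Table 2 also shows a fault before any calculation. At N = 40 and p0 = 0.1, the row c = 7 carries alpha 0.003 in the p1 = 0.25 block and alpha below 0.001 in the p1 = 0.30 block. Type I error depends on n, c and p0 only, so both entries cannot be right.

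This is the rule that decides whether a multicentre trial goes ahead. If its error rates are wrong, those weighing a go decision misjudge how often an ineffective programme would pass. There is also a doubt about the cutoff: the text says at least 9, but the quoted power belongs to at least 10. With exactly 9 responders the two readings give opposite decisions.

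**Working it through.** **Inputs**, all from section 2.5.2 except n, which is also in section 1.4: n = 40; continue if X ≥ 9; p0 = 0.10; p1 = 0.35; X binomial.

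**Formula.** P(X ≥ c; p) = Σ over k = c to 40 of C(40,k) p^k (1−p)^(40−k). This is alpha at p = p0 and power at p = p1.

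**Attempt to reproduce the stated pair (alpha < 0.001, power 94%)**

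| Reading | Alpha | Power at p1 = 0.35 |
|---|---|---|
| As written: X ≥ 9, p0 = 0.10 | 0.0155 | 0.970 |
| Strict: X > 9 (that is, ≥ 10), p0 = 0.10 | 0.0051 | 0.936 |
| X ≥ 12, p0 = 0.10 | 0.00038 | 0.795 |
| X ≥ 9, p0 = 0.05 | 0.00013 | 0.970 |
| X > 9, p0 = 0.05 | 0.00002 | 0.936 |
| Normal approximation, c = 9, p0 = 0.10, without / with continuity correction | 0.0042 / 0.0089 | 0.951 / 0.966 |
| Normal approximation, c = 10, p0 = 0.10, without / with continuity correction | 0.0008 / 0.0019 | 0.908 / 0.932 |
| Exact, n = 37, X ≥ 9, p0 = 0.10 | 0.0093 | 0.941 |

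At p0 = 0.10 and n = 40 the exact alpha is still 0.0015 at c = 11 and first drops below 0.001 at c = 12. No threshold therefore combines alpha < 0.001 with 94% power. The only reading above that gives the stated pair is X > 9 with p0 = 0.05, which departs from the text on both the inequality and p0.

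**Hand check of alpha.** One term of the sum is enough to refute it: P(X = 9; 0.10) = C(40,9) × 0.1^9 × 0.9^31 = 273,438,880 × 10^−9 × 0.03815 = 0.0104. This already exceeds 0.001 about tenfold. Adding P(X ≥ 10) = 0.0051 gives 0.0155.

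**Size of the understatement.** 0.0155 / 0.001 = 15.5, so the false-go rate is more than 15 times the stated bound.

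**N = 40 half of Table 2, row by row**

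| p1 | c | Printed alpha, power | Alpha, X ≥ c, p0 = 0.10 | Power, X ≥ c | Power, X > c |
|---|---|---|---|---|---|
| 0.25 | 6 | 0.013, 0.96 | 0.206 | 0.957 | 0.904 |
| 0.25 | 7 | 0.003, 0.90 | 0.100 | 0.904 | 0.818 |
| 0.25 | 8 | <0.001, 0.82 | 0.042 | 0.818 | 0.700 |
| 0.30 | 7 | <0.001, 0.94 | 0.100 | 0.976 | 0.945 |
| 0.30 | 8 | <0.001, 0.89 | 0.042 | 0.945 | 0.889 |
| 0.30 | 9 | <0.001, 0.80 | 0.016 | 0.889 | 0.804 |
| 0.35 | 9 | <0.001, 0.94 | 0.016 | 0.970 | 0.936 |
| 0.35 | 10 | <0.001, 0.88 | 0.005 | 0.936 | 0.879 |
| 0.35 | 11 | <0.001, 0.79 | 0.0015 | 0.879 | 0.795 |

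The printed powers follow X ≥ c in the p1 = 0.25 block and X > c in the other two. No printed alpha matches p0 = 0.10 under X ≥ c. Under X > c only the last row does (0.00038). At p0 = 0.05, P(X ≥ 6, 7, 8) = 0.0139, 0.0034, 0.0007, which are the printed alphas of the first block (0.013 by truncation). The other blocks are also below 0.001 at p0 = 0.05, with 0.0007 the largest value under X > c. The likely cause is therefore alphas computed at 5% under a 10% label, together with a change of tail convention within the table. This is an inference from the numbers; the document does not say so.

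**The case against.** The strongest objection is that nothing about the decision has to change. A true alpha of 0.0155 is low by any usual standard, power is higher than claimed, 40 patients remain enough, and the section sets no target alpha that could be breached. The factor of 15 compares two small probabilities. The worst table entry, c = 6, belongs to a threshold the plan does not adopt, and the p1 = 0.25 powers are correct as printed. All of this stands, and it limits the harm to a misstatement of the rule's properties.

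A second objection is that a p0 label may have been lost when the table was extracted, since the text says that 5% and 10% were both considered. That could explain the alphas, but it does not rescue the statement. The prose itself names p0 = 0.1 beside the same alpha and power, and power does not depend on p0, so a lost label cannot produce 94% for a rule of at least 9.

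Third, the intended p0 and inequality cannot be known from the document, and moving to at least 10 would change the rule and not merely correct a figure. This is right, and it determines the order of the fix.

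**Conclusion.** The concern holds. For the rule of at least 9 of 40, the exact type I error at p0 = 0.10 is 0.0155 against a stated value below 0.001, and power at p1 = 0.35 is 97.0% against 94%. No threshold at that p0 and sample size gives the stated pair. In the N = 40 half of Table 2 every alpha is wrong for the labelled p0 under the section's own definition, by as much as 0.206 against 0.013, and six of the nine powers use the other tail.

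The arithmetic rests only on inputs that the section states. The 97% takes 0.35 as the success rate among all 40, with drop-outs already counted as failures. If 0.35 were instead the rate among completers, 10% drop-out would give 0.35 × 0.9 = 0.315 and power 0.92, and 20% would give 0.28 and power 0.83. The rule and the sample size survive; the stated error rates do not.

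**What to change.** 1. Have the sponsor confirm, before outcome data are seen, that p0 is 0.10 and that 9 responders means continue.
2. If so, restate the sentence: with 40 patients and a rule of at least 9, type I error is 0.016 and power is 97% for p0 = 0.10 against p1 = 0.35.
3. If 94% power was the design intent, the rule is at least 10 (alpha 0.005). This changes the decision rule and should be recorded as such. If p0 = 0.05 was intended, say so (alpha 0.0001, power 97% at 9 or more).
4. Regenerate the N = 40 half of Table 2 with X ≥ c throughout; for p0 = 0.10 the values are the two X ≥ c columns above.
5. Correct the N = 12 half and the sentence on the 12 Hispanic participants in the same pass, because they also use X > c. At least 3 of 12 (0.10 against 0.45) gives 0.111 and 0.958, not 0.026 and 0.87. At least 2 of 12 (0.05 against 0.35) gives 0.118 and 0.958, not 0.02 and 0.85.

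The cost for the primary rule is one sentence and half a table; item 5 adds a sentence and the other half. Keeping at least 9 of 40 needs no extra patients. The stated alpha becomes less favourable but stays below 0.05.

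### Hispanic-subgroup rules (≥3 and ≥2 of 12): the stated error rates belong to thresholds one responder higher; true type I errors are 0.111 and 0.118, not 0.026 and 0.02

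*Combined protocol and SAP*

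**What the plan says.** Section 2.5.2 (Sample size) tests futility with the exact binomial distribution. It chooses "the largest value of c such that $P(X \geq c | p_0) \leq \alpha$, type I error", and defines power in the same way, as the probability of c or more responders under p1. Both definitions include c.

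For the Hispanic subgroup it then states: "For the 12 Hispanics, we would need ≥ 3 ($\alpha = 0.026$, $1-\beta = 0.87" for the first rule, "and ≥ 2 ($\alpha = 0.02$, $1-\beta = 0.85$) individuals to achieve 5% weight loss reject futility" for the second, "assuming $p_0 = 0.1$ vs $p_1 = 0.45$ and $p_0 = 0.05$ vs $p_1 = 0.35$, respectively". The N = 12 half of Table 2 repeats these pairs at c = 3 and c = 2.

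The same section says: "To be conservative, drop-outs will count as weight loss failures". The denominator therefore stays at 12 and needs no adjustment for loss to follow-up.

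**The concern.** With an expected 1.2 responders among 12 at p0 = 0.10 (12 × 0.10), three or more is not a rare event, so a type I error of 0.026 looks too small for that rule. The printed figures look like the probability of more than c responders, whereas the rule is worded and defined as c or more.

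At stake is the result at exactly the threshold. With 3 responders (p0 = 0.10) or 2 responders (p0 = 0.05), the wording rejects futility, while the quoted error rates describe a rule that would not. One responder is 1/12 = 8.3% of the subgroup. If this is noticed only after the data are in, the choice between the two readings could be made knowing the result.

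**Working it through.** **Inputs, all from section 2.5.2.** n = 12; rule 1: c = 3, p0 = 0.10, p1 = 0.45; rule 2: c = 2, p0 = 0.05, p1 = 0.35. X is binomial(12, p); type I error = P(X ≥ c | p0); power = P(X ≥ c | p1).

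**Rule 1 (≥3).**
- p = 0.10: P(0) = 0.9^12 = 0.2824; P(1) = 12 × 0.1 × 0.9^11 = 0.3766; P(2) = 66 × 0.1^2 × 0.9^10 = 0.2301. P(X ≥ 3) = 1 − 0.8891 = **0.1109**.
- Removing P(3) = 220 × 0.1^3 × 0.9^9 = 0.0852 gives P(X ≥ 4) = 0.0256, which is the printed 0.026.
- p = 0.45: P(0) + P(1) + P(2) = 0.0008 + 0.0075 + 0.0339 = 0.0421 (from unrounded terms), so P(X ≥ 3) = **0.9579**. Removing P(3) = 0.0923 gives P(X ≥ 4) = 0.8655, the printed 0.87.

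**Rule 2 (≥2).**
- p = 0.05: P(0) = 0.95^12 = 0.5404; P(1) = 12 × 0.05 × 0.95^11 = 0.3413. P(X ≥ 2) = 1 − 0.8816 = **0.1184** (from unrounded terms). Removing P(2) = 66 × 0.05^2 × 0.95^10 = 0.0988 gives P(X ≥ 3) = 0.0196, the printed 0.02.
- p = 0.35: P(0) + P(1) = 0.0057 + 0.0368 = 0.0424 (from unrounded terms), so P(X ≥ 2) = **0.9576**. Removing P(2) = 0.1088 gives P(X ≥ 3) = 0.8487, the printed 0.85.

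**All N = 12 rows of Table 2 (type I error, power).**

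| p0, p1 | c | Printed | P(X ≥ c) | P(X > c) |
|---|---|---|---|---|
| 0.10, 0.40 | 2 | 0.11, 0.92 | 0.341, 0.980 | 0.111, 0.917 |
| | 3 | 0.026, 0.77 | 0.111, 0.917 | 0.0256, 0.775 |
| | 4 | 0.004, 0.56 | 0.0256, 0.775 | 0.0043, 0.562 |
| 0.10, 0.45 | 2 | 0.11, 0.96 | 0.341, 0.992 | 0.111, 0.958 |
| | 3 | 0.026, 0.87 | 0.111, 0.958 | 0.0256, 0.866 |
| | 4 | 0.004, 0.70 | 0.0256, 0.866 | 0.0043, 0.696 |
| 0.05, 0.35 | 1 | 0.12, 0.96 | 0.460, 0.994 | 0.118, 0.958 |
| | 2 | 0.020, 0.85 | 0.118, 0.958 | 0.0196, 0.849 |
| | 3 | 0.002, 0.65 | 0.0196, 0.849 | 0.0022, 0.653 |

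Every printed pair agrees with P(X > c), and none with P(X ≥ c).

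**Other explanations tried.** A normal approximation does not reproduce the figures: for ≥3 the type I error is 0.042 without and 0.106 with continuity correction; for ≥2 it is 0.032 and 0.117. A broken table does not explain it either, because the running text repeats two of the pairs with an explicit ≥ sign.

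**The case against.** The arithmetic is not in dispute; the case on the other side is about weight.

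- **The decision to continue to a larger trial is tied to ≥9 of 40, not to the subgroup.** Hispanic participants do not appear in the objectives or in the statistical methods section, and the exact confidence intervals planned in section 2.5.3 do not depend on c. This stands and limits the consequence. Still, section 2.5.2 does present these thresholds as what is needed to reject futility in the subgroup.
- **Twelve is not fixed elsewhere as a recruitment target.** Section 3.13 only anticipates a high proportion of Hispanic participants in Arizona. If the final number differs, the rule must be recalculated anyway. That is true, but the recalculation would need the correct convention.
- **No maximum type I error is set for the subgroup, and Table 2 itself shows options at 0.11 and 0.12.** So 0.111 and 0.118 breach no stated limit, and the rules as worded miss a useful effect less often (about 4%, against the implied 13% and 15%). This also stands. It makes keeping the thresholds a legitimate choice, but it does not make the printed figures right.
- **The documents do not show whether the threshold, the inequality sign or the probabilities are the slip.** Agreed; what is certain is that they do not match.

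The N = 40 half of Table 2 has a separate mismatch: ≥9 at p0 = 0.10 and p1 = 0.35 gives type I error 0.0155 and power 0.970, against the stated <0.001 and 0.94. A shift of one explains the power (P(X > 9 | 0.35) = 0.936) but not the type I error (P(X > 9 | 0.10) = 0.0051). It is a further reason to recalculate the whole table.

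**Conclusion.** The concern holds. The subgroup thresholds and their stated error rates describe different rules, one responder apart.

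- **≥3 of 12:** type I error 0.111 against the stated 0.026 (0.111/0.026 = 4.3 times); power 0.958 against 0.87.
- **≥2 of 12:** type I error 0.118 against 0.02 (5.9 times); power 0.958 against 0.85.

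A reader who picks another row is misled further: c = 1 at p0 = 0.05 has type I error 0.460, not 0.12, and c = 2 at p0 = 0.10 has 0.341, not 0.11.

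This rests on n = 12, drop-outs counted as failures, independent binomial responses, and the plan's own inclusive definition of c. A pre-specified rule that contradicts its own error rates must be corrected, although the main decision for the trial rests on the full sample.

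**What to change.** Choose one of the following and record the choice before outcome data are seen.

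1. **Keep ≥3 and ≥2.** Restate type I error as 0.11 and 0.12, and power as 0.96 for both. The rule does not change; the plan then openly accepts a false-positive chance of 11 to 12% in the subgroup.
2. **Keep the stated error rates.** Change the thresholds to ≥4 (p0 = 0.10 versus p1 = 0.45) and ≥3 (p0 = 0.05 versus p1 = 0.35). This changes the rule and brings power down from 0.958 to 0.866 and 0.849, that is, to the values already printed.

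Under either option, raise each c in the N = 12 half of Table 2 by one (2, 3, 4 become 3, 4, 5; 1, 2, 3 become 2, 3, 4), or leave c and replace the entries with the P(X ≥ c) values above. Recalculate the N = 40 half at the same time.

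The cost is a correction to text and table. No extra participants, visits or data are needed.

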2.5.3. Statistical methods

Descriptive statistics will be generated for all study parameters (e.g. SD of change in ACT). Cross-sectional comparisons will be made using Kruskall-Wallis and Fisher's exact tests. We will determine the proportion of participants achieving a 5% weight loss with exact 95% confidence intervals. Mixed effects models will be used to analyze repeated measures.

3. Monitoring

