3.13. Inclusion of minorities

We anticipate Vermont and Arizona will reflect the demographics of these two regions, and anticipate recruiting a high proportion of Hispanics at the Arizona site.

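### The error rates printed for the 12 Hispanic participants belong to thresholds one higher than those stated, so the subgroup's type I error is understated about 4-fold and 6-fold.

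*Combined protocol and SAP*

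**What the plan says.** Section 2.5.2 describes an exact binomial rule. The threshold c is defined as "the largest value of c such that $P(X \geq c | p_0) \leq \alpha", with power as the same upper tail at p1. Drop-outs count as failures, so the denominator stays fixed.

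For all 40 participants the section names one pair (10% versus 35%), one threshold (at least 9) and one consequence: if at least 9 "individuals have clinically significant weight loss we would reject futility and continue on to a larger trial".

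For the subgroup it says "For the 12 Hispanics, we would need ≥ 3" (printed alpha 0.026, power 0.87) and then gives at least 2 (printed alpha 0.02, power 0.85), in order to "reject futility assuming $p_0 = 0.1$ vs $p_1 = 0.45$ and $p_0 = 0.05$ vs $p_1 = 0.35$, respectively". The N = 12 half of Table 2 repeats these pairs at c = 3 and c = 2. The table is described as being "for a variety of futility, p_0 , and minimum efficacy, p_1 , thresholds".

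Section 2.5.3 (Statistical methods) names no subgroup test. For the primary outcome it says: "We will determine the proportion of participants achieving a 5% weight loss with exact 95% confidence intervals".

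**The concern.** With only 12 people, moving the threshold by one changes the error rates a great deal. Under the definition given, a threshold of 3 when the true rate is 10% should carry a type I error well above 0.026, and a threshold of 2 at a true rate of 5% well above 0.02.

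If the printed rates belong to other thresholds, the subgroup assessment looks much stricter than it is. Anyone citing these figures to support a statement about Hispanic participants would be relying on a false-positive rate that the stated rule does not have. The section also never says whether the two thresholds are illustrations or whether one of them will be applied.

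**Working it through.** **Inputs** (all from section 2.5.2): n = 12; thresholds 3 and 2; pairs 0.10/0.45 and 0.05/0.35; rule P(X ≥ c) with X binomial.

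**Formula:** P(X ≥ c | p) = 1 − Σ C(12, k) p^k (1 − p)^(12 − k), summed over k = 0 to c − 1.

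**Threshold 3, 0.10 versus 0.45**
- At p = 0.10, P(0), P(1), P(2) = 0.2824, 0.3766, 0.2301. Alpha = 1 − 0.8891 = 0.1109 (printed 0.026).
- At p = 0.45, P(0), P(1), P(2) = 0.0008, 0.0075, 0.0339. Power = 1 − 0.0421 = 0.9579 (printed 0.87). The sum uses unrounded terms.

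**Threshold 2, 0.05 versus 0.35**
- At p = 0.05, P(0), P(1) = 0.5404, 0.3413. Alpha = 1 − 0.8816 = 0.1184 (printed 0.02). The sum uses unrounded terms.
- At p = 0.35, P(0), P(1) = 0.0057, 0.0368. Power = 1 − 0.0424 = 0.9576 (printed 0.85). The sum uses unrounded terms.

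**Reproducing the printed figures.** Removing one more term, so that the tail starts at c + 1, gives them.
- At least 4: alpha = 0.1109 − P(3) = 0.1109 − 0.0852, which is 0.0256 unrounded; power = 0.9579 − 0.0923, which is 0.8655 unrounded.
- At least 3: alpha = 0.1184 − P(2) = 0.1184 − 0.0988 = 0.0196; power = 0.9576 − 0.1088, which is 0.8487 unrounded.

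The normal approximation does not give the printed pairs. For threshold 3 it gives 0.042/0.918 without and 0.106/0.954 with continuity correction. For threshold 2 it gives 0.032/0.909 and 0.117/0.949.

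**The whole N = 12 half of Table 2** (alpha, power):

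| p0 | p1 | c | Printed | P(X > c) | P(X ≥ c) |
|---|---|---|---|---|---|
| 0.10 | 0.40 | 2 | 0.11, 0.92 | 0.111, 0.917 | 0.341, 0.980 |
| 0.10 | 0.40 | 3 | 0.026, 0.77 | 0.026, 0.775 | 0.111, 0.917 |
| 0.10 | 0.40 | 4 | 0.004, 0.56 | 0.004, 0.562 | 0.026, 0.775 |
| 0.10 | 0.45 | 2 | 0.11, 0.96 | 0.111, 0.958 | 0.341, 0.992 |
| 0.10 | 0.45 | 3 | 0.026, 0.87 | 0.026, 0.866 | 0.111, 0.958 |
| 0.10 | 0.45 | 4 | 0.004, 0.70 | 0.004, 0.696 | 0.026, 0.866 |
| 0.05 | 0.35 | 1 | 0.12, 0.96 | 0.118, 0.958 | 0.460, 0.994 |
| 0.05 | 0.35 | 2 | 0.020, 0.85 | 0.020, 0.849 | 0.118, 0.958 |
| 0.05 | 0.35 | 3 | 0.002, 0.65 | 0.002, 0.653 | 0.020, 0.849 |

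All nine rows match P(X > c) to rounding (the 0.775 is 0.7747 unrounded). None matches P(X ≥ c).

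**Size of the understatement:** 0.111 / 0.026 = 4.3 and 0.118 / 0.02 = 5.9.

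**Main rule, n = 40, 0.10 versus 0.35** (printed alpha below 0.001, power 0.94)
- At least 9: alpha 0.0155, power 0.970.
- More than 9: alpha 0.0051, power 0.936.

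The printed power fits more than 9. Neither inequality gives an alpha below 0.001 at p0 = 0.10. At least 9 does so at p0 = 0.05 (0.00013), which is not the null rate stated for this rule.

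**The case against.** The arithmetic has no good counter-argument. Damage to the text in conversion is an unlikely explanation: the at-or-above sign appears in the definition, in the main rule and at both subgroup thresholds, and the sentence and the table print the same pairs.

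The stronger objection is about consequence, and most of it stands. A reader might infer that the plan contains two competing futility rules for Hispanic participants, so that 2 of 12 would pass one and fail the other. The documents do not support that as the main reading. The sentence sits under sample size, ties each threshold to its own pair of rates, and draws on a table that is openly a set of alternatives. Two design scenarios is the likelier meaning. What remains is that the plan neither labels them as scenarios nor selects one.

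A reader might also infer that the trial could be stopped, or the larger trial blocked, by the subgroup result. Nothing supports this. The only stated action depends on at least 9 of 40, the objectives name no Hispanic hypothesis, and section 2.5.3 adds no subgroup test.

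Finally, one might judge the threshold paired with 45% by its performance at 35%, since the section says "A significant proportion of the population is set at 35" per cent. That takes a scenario outside its own assumptions and does not show an error. Removing the subgroup thresholds altogether would be a choice for the sponsor; the error does not require it.

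**Conclusion.** The concern holds as an error in the stated operating characteristics. With the plan's own inequality, the two subgroup thresholds have type I error of 0.111 and 0.118, not 0.026 and 0.02, and power of 0.958 in both cases, not 0.87 and 0.85. The printed pairs describe thresholds one higher.

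This rests on exact binomial tails, n = 12 with drop-outs kept as failures, and the pairs of rates as printed. The documents do not show whether the thresholds or the error rates were intended, so either could be the part to correct.

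The correction should be made, but it is limited in scope: it concerns what may be said about the subgroup and leaves the go decision where it is. The figures printed for that decision's own rule also fail to reproduce and should be checked together with these.

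**What to change.** 1. State in section 2.5.2 whether the rule is at least c or more than c, and use it throughout.
2. Then do one of the following:
   - keep at least 3 and at least 2, and print 0.111/0.958 and 0.118/0.958; or
   - keep the printed rates, and restate the thresholds as at least 4 and at least 3.
3. Make the N = 12 half of Table 2 agree, either by replacing its figures with the P(X ≥ c) column above or by raising each c by one.
4. Add one sentence on the status of the subgroup figures. If they are scenarios, say so and report the Hispanic proportion with the exact 95% confidence interval already planned in section 2.5.3. If a subgroup futility conclusion is intended, name one pair of rates and one threshold before data are seen.
5. Confirm the inequality for the main rule and print its exact rates: 0.0155 and 0.970 for at least 9 of 40, or 0.0051 and 0.936 for more than 9.

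The cost is a few sentences and corrected table entries, with no extra participants. The downside is that either the stated subgroup alpha becomes less favourable or the subgroup threshold rises by one.
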